4.2.3 Analysis methods for exploratory outcome variables

All analyses of the exploratory outcome variables will be conducted with the full analysis set.

4.2.3.1

CCI

[REDACTED]

4.2.3.2 CCI [REDACTED]

[REDACTED]

[REDACTED]

[REDACTED]

[REDACTED]

4.2.3.3 Oral corticosteroid management

The exploratory endpoint used to evaluate the effect of the anifrolumab regimens versus placebo on the ability to achieve a sustained reduction of OCS dose is the difference in proportions of subjects able to taper OCS to ≤ 7.5 mg/day prednisone-equivalent by Week 24 and maintain this dose through Week 52. The effect of the anifrolumab regimens versus placebo will also be evaluated on the ability to achieve a sustained reduction of OCS dose using the difference in proportions of subjects able to taper OCS to ≤ 5.0 mg/day prednisone-equivalent by Week 80 and maintain this dose through Week 104.

The same CMH approach as described in Section 4.2.2 will be used to estimate the treatment differences between the anifrolumab regimens and placebo at Week 52 and at Week 104. Any missing data will be imputed as defined in Section 4.1.4.

Subgroup analyses will be performed as described in Section 4.3.

Reduction of OCS dose will also be assessed at Week 24 by examining the proportions of subjects able to taper OCS to ≤ 7.5 mg/day prednisone-equivalent by Week 24, using the same analysis approach. Reduction of OCS dose will also be assessed at Week 80 by examining the proportions of subjects able to taper OCS to ≤ 5.0 mg/day prednisone-equivalent by Week 80, using the same analysis approach.

In order to examine the impact of missing data, a tipping point analysis as described in Section 4.2.2 will also be performed for the sustained reduction of OCS dose at Week 52 and Week 104. The analysis for each treatment group, and the pooled anifrolumab group, will only be statistically interpreted if the nominal p-value from the main analysis of sustained reduction of OCS dose detailed above, for the respective comparison with placebo at the specified visit, is <0.05 (in favour of anifrolumab).

Daily OCS doses and changes from baseline will be presented by descriptive statistics by visit for all subjects.

Additionally, the daily OCS dose will be displayed graphically by a longitudinal plot presenting the means and corresponding SDs. The number of subjects will also be included in the graph.

Shift plots (scatter plot) for the daily OCS dose presenting baseline values versus Week 24 values, baseline values versus Week 52 values and Week 52 values versus Week 104 values will also be provided. A diagonal line indicating no change will be included in this shift plot.

Furthermore, the standardised AUC up to Week 52, up to Week 104 and from Week 52 to Week 104 will be summarised by treatment group for all subjects.

4.2.3.4 Renal response modified to include oral corticosteroid tapering requirement

The renal response endpoints CRR and PRR will be modified to include an OCS tapering requirement and used to evaluate the effect of anifrolumab on renal response.

The same CMH approach as described in Section 4.2.2 will be used to estimate the treatment differences between the anifrolumab regimens and placebo at Week 52 and at Week 104. Any missing data will be imputed as defined in Section 4.1.4. Modified CRR and PRR will also be assessed at Week 24 by examining the proportions of subjects who achieve CRR/PRR and are also able to taper OCS to ≤ 7.5 mg/day prednisone-equivalent by Week 24, using the same analysis approach.

A bar plot showing the proportion of subjects who achieve modified CRR or PRR by treatment group (including CIs and number of subjects included in the analysis) will be provided for both Weeks 24 and 52.

4.2.3.5 CCI

[Redacted content]

4.2.3.6 CCI [Redacted]

[Redacted]

[Redacted]

[Redacted]

4.2.3.7 CCI [Redacted]

[Redacted]

[Redacted]

[Redacted]

[Redacted]

4.2.3.8 CCI [Redacted]

[Redacted]

[REDACTED]

[REDACTED]

4.2.3.9 CCI [REDACTED]

[REDACTED]

[REDACTED]

4.2.3.10 SLEDAI-2K

Change from baseline in SLEDAI-2K will be evaluated using the same summaries and analysis approach except SLEDAI-2K data will not be log transformed, as specified in Section 4.2.3.5, with the appropriate substitution for the baseline value.

4.2.3.11 Non-renal SLEDAI-2K

Change from baseline in non-renal SLEDAI-2K will be evaluated using the same summaries and analysis approach except non-renal SLEDAI-2K data will not be log transformed, as specified in Section 4.2.3.5, with the appropriate substitution for the baseline value.

4.2.3.12 Physician global assessment

Change from baseline in PGA will be evaluated using the same summaries and analysis approach except PGA data will not be log transformed, as specified in Section 4.2.3.5, with the appropriate substitution for the baseline value.

4.2.3.13 SLICC/ACR Damage Index

Change from baseline in SDI will be evaluated using the same analysis approach and summaries (except that SDI data will not be log-transformed) as specified in Section 4.2.3.5, with the appropriate substitution for the baseline value. SDI will also be analysed by baseline SDI (≥ 1 vs 0).

4.2.4 Subject reported outcome variables

4.2.4.1 Patient Global Assessment

Change from baseline in PtGA will be evaluated using the same summaries and analysis approach except PtGA data will not be log transformed, as specified in Section 4.2.3.5, with the appropriate substitution for the baseline value.

4.2.5 Presentation of study population

4.2.5.1 Subject disposition

The number and percentage of subjects randomised, randomised but not treated with IP, and not randomised will be summarised by treatment group for the all subjects analysis set.

The number and percentage of subjects completing the double-blind treatment period of the study up to and including Week 52 and the number and percentage of subjects withdrawing from the study during the double-blind treatment period including reason for withdrawal, will be summarised by treatment group for the full analysis set .

The number and percentage of subjects completing treatment with IP during the double-blind treatment period up to and including Week 48 (i.e. with last administration of IP at Visit 13), the number and percentage of subjects permanently discontinuing the treatment with IP during the double-blind treatment period including reason for withdrawal, and the number and percentage of subjects who discontinued the treatment with IP after completing treatment with IP in the double-blind treatment period and did not enter the second year extension period including reason for withdrawal, will be summarised by treatment group for the full analysis set.

The number and percentage of subjects continuing into the second year extension period of the study from Week 52 up to and including Week 112 will be summarised by treatment group for the full analysis set.

The number and percentage of subjects completing the second year extension period of the study from Week 52 up to and including Week 112 and the number and percentage of subjects withdrawing from the study during the second year extension period including reason for withdrawal, will be summarised by treatment group for subjects who continued in the second year extension period.

The number and percentage of subjects completing treatment with IP during the second year extension period from Week 48 up to and including Week 100 (i.e. with last administration of IP at Visit 26) and the number of subjects permanently discontinuing the treatment with IP during the second year extension period including reason for withdrawal, will be summarised by treatment group for the subjects who continued into the second year extension period.

The number and percentage of subjects not continuing into the second year extension period of the study including reason for not continuing, will be summarised by treatment group for the full analysis set.

The number and percentage of subjects completing the study up to and including Week 112 and the number and percentage of subjects withdrawing from the study including reason for withdrawal, will be summarised by treatment group for the full analysis set.

The number and percentage of subjects completing treatment with IP up to and including Week 100 (i.e. with last administration of IP at Visit 28) and the number of subjects

permanently discontinuing the treatment with IP including reason for withdrawal, will be summarised by treatment group for the full analysis set.

A summary of number and percentage of subjects in each country and each site by treatment group and overall will be provided for the full analysis set.

Summaries of important protocol deviations and analysis sets will be provided.

4.2.5.2 Demographic and baseline characteristics

Demography and baseline characteristics will be presented by descriptive statistics by treatment group as well as overall for the full analysis set.

Stratification factors at randomisation will be presented by descriptive statistics by treatment group as well as overall for the full analysis set.

Past and current medical history will be summarised separately by MedDRA system organ class and preferred term. Surgical history will be listed.

Prior and concomitant medications will be summarised separately by WHO Drug Dictionary ATC classification (ATC level 1), and preferred term. A summary of disallowed concomitant medication taken on or after the date of first dose of study treatment which would lead to the classification of a subject as a non-responder will be provided, splitting into medications received while on IP or while off IP, based on medication start date. For subjects having prematurely discontinued IP, medications received after IP initiation and before or on the date of last IP administration will be considered “on IP”. However, for subjects who have a last infusion of IP within the Week 48 analysis visit window, medications received after IP initiation and before or on the date of Week 52 (or the date of Week 48 + 28 days in case that Week 52 was missed) will be considered “on IP”. Medications received after the date of last IP administration, in case of premature IP discontinuation will be considered to be “off IP”.

A summary of ACE inhibitors and ARBs taken during the study will be presented separately. A list of preferred terms for inclusion in this summary will be finalised and agreed prior to study database lock and unblinding.

4.2.5.3 Exposure

Exposure will be summarised by treatment group for the full analysis set.

Summary statistics will be provided for the cumulative duration of exposure. The number and percentage of subjects treated ≥ 4 weeks, ≥ 8 weeks, and up to 104 weeks in 4-weekly intervals will be provided.

The number and percentage of subjects with infusions will be presented by total number of infusion (i.e. 1, 2, ..., 13) and in 4-weekly intervals (i.e. 4 weeks, 8 weeks, 12 weeks, ..., 100 weeks).

Furthermore, the time to discontinuation of IP will be presented as Kaplan-Meier plot including the number of subjects at risk (i.e. still on IP).

Subjects with complications (e.g. an interruption) in any infusion will be presented in a listing.

4.2.6 Analysis methods for safety variables

Safety variables will be summarised by treatment group for the full analysis set.

4.2.6.1 Adverse Events

If not stated otherwise, all summaries described below will be presented separately for

- AEs during treatment
- AEs during follow-up

For summaries during follow-up, only subjects with any study documentation after the date of last dose of IP + 28 days will be considered.

An overall summary of subjects with at least one AE in the following categories will be presented, and will include the event rate per 100 subject years, and total exposure in years for each treatment group:

- Any AE
- Any acute AEs
This category will not be included in the summary during follow-up.
- Any AE with outcome = death
- Any SAE (including events with outcome = death)
- Any AE leading to discontinuation of IP
 - This category will not be included in the summary during follow-up.
- Any AE related to IP by investigator's judgement
- Any AE of severe intensity
- Any AESI
 - Any AESI of non-opportunistic serious infections
 - Any AESI of opportunistic infections
 - Any AESI of anaphylaxis
 - Any AESI of malignancy
 - Any AESI of herpes zoster
 - Any AESI of tuberculosis
 - Any AESI of influenza
 - Any AESI of vasculitis (non-SLE)
 - Any AESI of major acute cardiovascular events (MACE as adjudicated)
- Any other significant AE

The number and percentage of subjects with at least one AE (i.e. multiple occurrences of an AE in 1 subject will only be counted once) will be summarised by MedDRA system organ class and preferred term (unless specified otherwise) for the following AE categories. These summaries will also include the event rate per 100 subject years and total exposure in years for each treatment group (unless specified otherwise).

- Any AE
- Any AE above reporting threshold of 2% of subjects in any treatment group in the full analysis set.
This summary will be presented by preferred term for AEs during treatment only.
- Any non-serious AE above reporting threshold of 5% of subjects in any treatment group in the full analysis set
This summary will not include the event rate per 100 subject years and total exposure in years.
- Any SAE with outcome = death
This summary will be presented for SAEs with an outcome of death during the treatment and follow-up periods combined.
- Any SAE (including events with outcome = death)
- Any AE leading to discontinuation of IP
This summary will be presented for AEs during treatment only.
- Any AE by relationship to IP (yes, no)
(multiple occurrences of an AE in 1 subject will only be counted once as related if at least one AE is related and as not related if all occurrences are not related)
This summary will be presented for AEs during treatment only.
- Any AE by maximum intensity (mild, moderate, severe)
(i.e. multiple occurrences of an AE in 1 subject will only be counted once with the maximum intensity in this AE)
This summary will be presented for AEs during treatment only.
- Any AESI
This summary will not be presented by system organ class but by AESI category (non-opportunistic serious infections, opportunistic infections, anaphylaxis, malignancy, herpes zoster, tuberculosis, influenza and vasculitis [non- SLE]).
- Any other significant AE
This summary will be presented for AEs during treatment only.
- Any AE by time interval (as detailed in Section 3.6.1) for the first onset of event
This summary will be presented for AEs during treatment only.

Cardiovascular outcome events as determined by the Cardiovascular Event Adjudication Committee will be presented separately, summarising the number of AEs submitted for adjudication and the outcomes of the adjudication including MACE classification. Site reported cardiovascular AEs, cardiovascular SAEs and their corresponding adjudicated outcomes will be listed.

The time to first onset of herpes zoster during treatment will be presented as a Kaplan-Meier plot including the number of subjects at risk at each visit.

Furthermore, the alternative event rates per 100 subject years for herpes zoster (and possible other AESIs) will be summarised for events during screening, during treatment, and during follow-up. The total time at risk will also be presented.

An overall summary of subjects with AE's in pre-specified categories will also be presented by ADA category.

Key subject information for subjects with an AE with outcome of death, subjects with serious AEs, subjects with an AE leading to discontinuation of IP, subjects with cardiovascular events and subjects with AESIs, respectively, will be provided.

All AEs and AEs in ADA positive (at any time) subjects will be listed.

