3.8.2.1 Major surgeries

Pre-operative management of IP: If a non-urgent major surgery becomes necessary during the study, it should be scheduled at least 4 weeks after the last administration of IP, if clinically feasible. The determination of whether or not a surgery is "urgent" will be at the discretion of the investigator, preferably in consultation with the Sponsor/Designee Medical Monitor.

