6.11.2 Infections

When an infection is reported as an SAE or AESI, cultures should be obtained and culture results should be reported with the event. Other specific laboratory or other investigations (eg, chest X-ray for pneumonia) that confirm or aid in the diagnosis or treatment should be

obtained when indicated and results should be reported with the SAE or AESI. Failure to obtain this information will impair the Sponsor's ability to characterise the benefit-risk profile of anifrolumab.

Subjects who develop a new infection while undergoing treatment with IP should receive appropriate medical therapy, as determined by local standards, and be monitored closely until the condition resolves. IP should not be administered to a subject with a clinically significant, active infection as determined by the Investigator (see Section 3.8). For any active infection (eg, *Varicella zoster* infection/chickenpox) or significant exposure to any infection (eg, *Varicella zoster* infection in a naive subject, bacterial pneumonia), the Investigator should consider whether to interrupt IP administration, and should notify the Sponsor/Designee Medical Monitor.

Similarly, if a subject presents with signs or symptoms where opportunistic infections are considered (eg, Central nervous system symptoms consistent with progressive multifocal leukoencephalopathy or herpes encephalitis, or atypical pneumonia suggesting pneumocystis jiroveci pneumonia), IP should be interrupted until the Principal Investigator confirms the symptoms and signs of infection have resolved or that no active infection has developed.

If dosing is resumed after resolution of a safety concern (ie, infection or other AE) the IP must be administered within 14 days of the scheduled time of the missed dose. If this is not possible, dosing should be resumed at the time of the next scheduled dose.

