3.6.1 Adverse events

Adverse events experienced by the subjects will be collected throughout the entire study, including the second year extension period, and will be coded using the latest version of MedDRA.

Adverse event data will be categorised according to their onset date into the following study periods:

- AEs occurring during screening:
An AE during screening is defined as an AE with a date of onset \geq date of the screening visit and date and time of onset $<$ date and time of the first dose of IP.
AEs occurring during screening will only be listed.
- AEs occurring during treatment:
An AE during treatment is defined as an AE with a date and time of onset \geq date and time of first dose of IP and \leq date of last dose of IP + 28 days.
- AEs occurring during follow-up:
An AE during follow-up is defined as an AE with a date of onset $>$ date of last dose of IP + 28 days and \leq date of last dose of IP + 84 days.
- AEs occurring after follow-up:
An AE after follow-up is defined as an AE with a date of onset $>$ date of last dose of IP + 84 days.
AEs occurring after follow-up will only be listed.

If an AE has a missing onset date, then unless the stop date of the AE indicates otherwise, this will be considered as an AE during treatment. Similarly, if an AE has a partial onset date, then unless the partial onset date or the stop date indicates otherwise, this will be considered an AE during treatment.

Adverse events with missing intensity will be assumed to be severe. Events with missing relationship to study medication per the investigator will be assumed to be related. If no information about seriousness is available, the AE will be considered serious.

An acute AE is defined as an AE with a date of onset on any day of administration of IP and a time of onset on or after the start of administration of IP or a date of onset occurring on the subsequent day. If an AE has a missing onset date, then unless the stop date of the AE indicates otherwise, this will be considered as an acute AE. Similarly, if an AE has a partial onset date, then unless the partial onset date or the stop date indicates otherwise, this will be considered acute AE.

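### Both tables of AEs leading to discontinuation of IP stop at last dose + 28 days, so a new AE that starts later in a longer dosing gap and ends treatment is counted in neither

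*SAP*

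**What the plan says.** SAP 3.6.1 assigns each AE to a period by its onset date. For the treatment period it begins "An AE during treatment is defined as an AE with a date and time of onset" at or after the first dose, and it sets the upper limit at "date of last dose of IP + 28 days". The follow-up definition ("An AE during follow-up is defined as an AE with a date of onset") takes over the next day and runs to day 84 after the last dose. Later AEs are only listed.

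SAP 4.2.6.1 then specifies two count tables that include AEs leading to discontinuation of IP.

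- **Overall AE summary.** The category "Any AE leading to discontinuation of IP" carries the note "This category will not be included in the summary during follow-up".
- **Table by system organ class and preferred term.** For the same category the note is "This summary will be presented for AEs during treatment only".

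There is no follow-up version and no combined version. Deaths, in the same section, do have a table for treatment and follow-up combined.

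The protocol does not hold dosing to exact 28-day steps. Tables 2 and 4 allow ±7 days per visit. Section 6.11.2 lets a dose held for a safety concern be given within 14 days of its scheduled time, and adds: "If this is not possible, dosing should be resumed at the time of the next scheduled dose". Section 4.2.1.2 and Table 4 allow the first extension dose as late as Week 60.

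**The concern.** The treatment period is fixed backwards from the last dose. When an AE ends treatment, the last dose is by definition the one given before the AE. With doses exactly 28 days apart, any AE that starts before the next dose falls inside the window. With a longer gap, an AE that starts on day 29 or later and stops IP is relabelled as a follow-up AE, although the subject had not stopped IP when it began. The discontinuation category does not exist for that period.

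The number and rate of AEs that ended treatment is a main tolerability result, shown by arm. A rule that can only remove cases makes it too low or leaves it unchanged. The disposition tables in SAP 4.2.5.1 count permanent IP stops by reason with no AE-onset window, so two tables in the same report may give different numbers, and no reconciliation is planned.

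**Working it through.** The plan states no figure to reproduce. The check applies the period rule to the dosing gaps that the protocol allows.

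**Rule (SAP 3.6.1).** With d = days from last dose to AE onset: d ≤ 28 is treatment; 29 to 84 is follow-up; above 84 is listed only. For a gap of G days between the last dose and the next planned dose, the days on which a treatment-ending AE would be missed number max(0, G − 28).

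| Situation | Source | Gap G | Days beyond day 28 |
|---|---|---|---|
| On schedule | Q4W dosing | 28 | 0 |
| Next visit 7 days late | Protocol Tables 2 and 4 | 35 | 7 |
| Last dose 7 days early, next visit 7 days late | Protocol Tables 2 and 4 | 42 | 14 |
| Held dose given 14 days late | Protocol 6.11.2 | 28 + 14 = 42 | 14 |
| Dose skipped to the next scheduled one | Protocol 6.11.2 | 2 × 28 = 56 | 28 |
| First extension dose at Week 52 + 14 days | Protocol 4.2.1.2, Table 4 | (365 + 14) − 337 = 42 | 14 |
| First extension dose at Week 60 | Protocol 4.2.1.2, Table 4 | 421 − 337 = 84 | 56 |

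The last two rows use the scheduled study days 337 (Week 48), 365 (Week 52) and 421 (Week 60).

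**Share missed through visit drift alone.** This is an assumption, because the documents give no distribution of actual visit dates. Let the two visits be off schedule by independent whole-day amounts, uniform on −k to +k, with n = 2k + 1 values each. The gap is L = 28 + D, where D is the difference of the two offsets, so E[L] = 28. With AE onset spread evenly over the gap, the share missed is E[max(D, 0)] / 28, where E[max(D, 0)] = Σ d(n − d) / n² for d = 1 to n − 1.

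- k = 7, n = 15: 560 / 225 = 2.49 days; 2.49 / 28 = 8.9%. The chance that a gap exceeds 28 days is 105 / 225 = 46.7%.
- k = 3, n = 7: 56 / 49 = 1.14 days; 1.14 / 28 = 4.1%.
- k = 2, n = 5: 20 / 25 = 0.80 days; 0.80 / 28 = 2.9%.

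With the last dose on its nominal day and only the next visit uniform over ±7 days, E[max(D, 0)] = (1 + 2 + … + 7) / 15 = 28 / 15 = 1.87 days, and 1.87 / 28 = 6.7%.

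**In subjects.** The plan has about 2 × 50 = 100 anifrolumab subjects. Assuming, for illustration, 10 treatment-ending AEs among them, the expected loss is 10 × 0.029 = 0.3, 10 × 0.041 = 0.4 or 10 × 0.089 = 0.9. It scales in proportion to the assumed 10. Late, skipped and Week 60 doses would add to this by an amount that cannot be estimated.

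**The case against.** The strongest reply is that little is lost and nothing is hidden. Most of it stands.

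- **Other outputs.** A reader might infer that these AEs disappear from the report or survive only in a listing. They do not. With onset up to day 84 they enter the follow-up summaries of any AE, and of SAEs or AESIs where they qualify. Key subject information is planned for subjects with an AE leading to discontinuation, with no onset window stated. The disposition table can show an AE as the reason for stopping. What no output gives is a complete count of AEs that ended IP.
- **Dose holds.** A reader might infer that infection holds feed the loss directly. Usually they do not: the infection that caused the hold normally began before the scheduled dose, so by day 28 if dosing was on time, and it is counted if it ends treatment. Only a new AE that starts later in the gap is missed. AEs with missing onset dates, or with partial dates that do not settle the period, default to treatment and are counted as well.
- **Surgery.** Protocol 3.8.2.1 says of non-urgent major surgery that "it should be scheduled at least 4 weeks after the last administration of IP", which may suggest that postoperative complications are systematically excluded. That route is remote. Major surgery planned during the study is an exclusion criterion, section 3.8.2 says planned surgery should be avoided where feasible, and the complication would itself have to end IP permanently.
- **Size.** The 9% needs both visits to use the whole ±7-day tolerance and onset to be even. Infusion reactions cluster at the infusion and are always counted, which lowers the share. Findings dated to a late pre-dose visit work the other way.
- **Between-arm bias.** None is shown. The rule is the same in every arm, and no efficacy or alpha-controlled result is affected.

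None of this removes the gap: the two tables that carry this category leave out a definable set of qualifying AEs.

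**Conclusion.** The point holds as a table-specification defect of modest size. For a treatment-ending AE with onset on day 29 or later after the last dose, both count tables in SAP 4.2.6.1 leave it out by stated rule, and the protocol allows on-IP gaps of 35 to about 84 days in which this can happen. The count can therefore be too low, and it may disagree with disposition. It need not: no difference arises unless such an AE occurs, and the two counts can differ for other reasons, for example when a subject stops by own decision because of an AE.

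The number missed is unknown because the documents give no rate of delayed doses. Under even onset and uniform visit drift it is about 3% (±2 days), 4% (±3 days) or at most about 9% (full ±7 days) of treatment-ending AEs, so probably zero to one subject through visit drift. The documents do not support a claim of concealed events, of a difference between arms, or of a large understatement. The change is still worth making, because the category is a main tolerability result, small counts are sensitive to one case, and the remedy is cheap.

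**What to change.** In SAP 4.2.6.1, in both the overall summary and the table by system organ class and preferred term:

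1. Present the number and percentage of subjects with any AE leading to discontinuation of IP for treatment and follow-up combined, that is, any onset after the first dose. The death table already combines the two periods, and Protocol 6.5.3 already collects the action taken with IP for each AE, so no new data are needed.
2. For this category, either omit the rate per 100 subject-years or compute it with time at risk that covers the added onset period. SAP 3.6.1 cuts exposure at last dose + 28 days, so adding later events to the existing rate would put events in the numerator that lie outside the denominator.
3. Cross-check the total against IP stops due to AE in the disposition table of SAP 4.2.5.1 and explain any differences.

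The cost is a short SAP edit, a filter change in two tables and a decision on the rate. The reported count may become slightly less favourable.
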